#### 5.5.9. Visit Windows

Data will be analyzed according to the nominal time points. Visit windows will not be used.

#### 5.5.10. Decay Corrected Dose at Time of Administration

The calculations in this section will need to be performed for the pre- and post- injection values for F-DCFPyL administration as well as pre- and post- injection from the Syringe to the flask for reference values.

If a decay correction was performed for the pre-or post- dose values then Correction Factor =1. Otherwise:

```
 \text{Correction Factor} = e^{(\ln(2)*(pre\ or\ post\ injection\ time(min)-injection\ time\ (min)))}/_{110\ min}
```

where the above formula will be calculated for each of the following pre and post injection times:

pre-dose

post dose

syringe prior to flask syringe post flask

start of measurement times with each PK period

Convert all pre- and post- injection amounts to mCi: 37MBq = 1mCi

If there was no post decay correction then:

```
Decay Corrected Dose at time of Administration = (pre injection amount (mCi)*Correction Factor Pre Dose)- \frac{Post\ injection\ amount\ (mCi)}{Correction\ Factor\ Post\ Dose}
```

If there was a post decay correction then:

Decay Corrected Dose at time of Administration(mCi) = (pre injection amount(mCi) – post injection amount(mCi))

Calculate decay corrected doses at time of administration in both mCi for all subjects and MBq for all subjects.

The Decay corrected pre-injection Reference Standard of syringe prior to injection into flask = amount (μCi) in syringe prior to injection into flask\*Correction Factor of syringe prior to flask.

The Decay corrected post-injection Reference Standard of syringe after injection into flask = amount ( $\mu$ Ci) in syringe after injection into flask\*Correction Factor of syringe after flask.

The decay corrected reference standards are only needed in µCi.

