9.5. Study Drug Preparation

The final drug product is supplied to each institution on the day of administration in a unit-dose syringe with no additional preparation required. Institutional policies and standard operating procedures (SOPs) should be followed for receipt and appropriate radiation safety handling. Before and after each administration, measure the amount of radioactivity in the syringe using an appropriate dose calibrator. Apply decay correction if necessary and calculate the administered dose accordingly.

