#### 7.7.4. PK

Blood, plasma, and urine collection at each nominal time will be collected twice per patient. The mean of the values at each nominal time will be used in the creation of parameters used in the analysis. For each subject, blood concentration-time data using actual blood draw times rather than nominal times will be computed by non-compartmental analysis and pharmacokinetic parameters will be generated. Additional blood concentration-time data will be fitted into a two-compartment model to calculate  $T_{1/2\text{-alpha}}$  and  $T_{1/2\text{-beta}}$ . Summary statistics for blood will be presented for maximum concentration ( $C_{max}$ ), area under the (activity-time) curve (AUC), body weight normalized clearance (CL), volume of distribution at steady-state ( $V_{ss}$ ), time to maximum concentration ( $T_{max}$ ), half-life( $T_{1/2}$ ) [noncompartmental analysis],  $T_{1/2}$ -alpha and  $T_{1/2}$ -beta [2-

compartment modelling], and mean residence time (MRT). Since there are two values collected per nominal time, the mean of these values within nominal time will be derived prior to generating the PK parameters. These PK parameters will be derived by an external analyst then summarized for the PK blood set. PSA groups, eGFR groups and eGFR will also be summarized for the PK blood set.

Summary statistics for urinary excretion will be presented for Tmax, Rate max, Rate last, T1/2elim, and Cumulative Urine Recovery. For % of injected dose recovered per each urine collection interval per subject will be used to calculate Tmax, Rate max, Rate last, T1/2elim, and cumulative urine recovery by 4 and 8 hours post-administration if feasible. These PK parameters will be derived by an external analyst then summarized for the PK urine set. eGFR groups as defined in Section 5.5.16 and eGFR will also be summarized for the PK urine set.

The ratio of plasma-to-blood concentrations will be calculated per subject/time-point.

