## 8.2. Exposure to Study Drug

Exposure to study drug will be summarized using summary statistics for volume administered, location of injection, correction factor at pre and post dose, the decay corrected dose in mCi and MBq at time of administration, and any dose change due to an AE for the safety set.

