#### 9.1. Derived Data

- Concentration of Reference Standard, µCi/mL =
  - (Decay Corrected pre injection reference standard of syringe prior to injection into flask—Decay Corrected post injection reference standard of syringe after injection into flask)/1000mL.
- Reference Standard CPM = F-DCFPyL reference standard (CPM) from PK\*Decay Correction factor for measurement time defined for 0-4 hours
- Average CPM for Reference standard= Average of 3 CPM results collected for F-DCFPyL std for 0-4 hours.
- Average CPM/ml for reference standard= Average CPM for reference standard/0.3
- Concentration of Reference Standard in CPM/ $\mu$ Ci = Average CPM/ml for reference standard/concentration of reference standard ( $\mu$ Ci/mL)
- For each blood, plasma and urine sample time, calculate:
  - $^{18}$ F-DCFPyL CPMb =  $^{18}$ F-DCFPyL CPM result at sample time\*correction factor for measurement time defined for the PK period the sample is drawn in
  - $CPM_b(ml) = CPM_b/0.3$

- CPM concentration( $\mu$ Ci/ml) = CPMb (ml) / Concentration of Sample in CPM ( $\mu$ Ci)
- Average CPM  $\mu$ Ci/ml = average CPM  $\mu$ Ci/ml within each unique nominal time
- Ratio of plasma to blood = Average CPM ( $\mu$ Ci/ml) for plasma/ Average CPM ( $\mu$ Ci/ml) for blood per unique sample nominal time
- For each urine sample, calculate:
  - Radioactivity excreted per collection interval ( $\mu$ Ci) = CPM ( $\mu$ Ci/ml) from urine\*urine collection volume (ml)
  - % Dose excreted = (Sum of Radioactivity exerted per collection interval( $\mu$ Ci) /(administered dose(mCi)\*1000))\*100
  - Average % dose excreted = average of individual % dose excreted per unique urine collection interval
  - Cumulative Average % dose excreted = sum of average % dose excreted over all unique urine collection intervals:
    - 0-4 hours = sum of average % dose excreted over 0-2 and 2-4 hours urine collection intervals
    - 0-8 hours = sum of average % dose excreted over all unique 0-2 and 2-4 hours urine collection intervals (0-2, 2-4, and 4-8 hours)

\_

Pharmacokinetic analyses will be conducted on pooled cohorts using the PK blood set and PK urine set.

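### The administered-activity formula in SAP 5.5.10 divides the uncorrected syringe residual by a decay factor that should multiply it, and its second branch leaves out an uncorrected pre-injection reading

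*SAP*

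**What the plan says.** SAP 5.5.10 defines one correction factor for every reading. Its exponent is ln 2 times the reading time minus the injection time, with a 110-minute half-life. A reading that was already corrected gets a factor of 1: "If a decay correction was performed for the pre-or post- dose values then Correction Factor =1".

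The dose is then derived in two branches.

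- If the residual was not corrected, the dose is "pre injection amount (mCi)*Correction Factor Pre Dose" minus the post-injection amount divided by the post-dose factor.
- "If there was a post decay correction then" the dose is the pre-injection amount minus the post-injection amount, with no factor on either.

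The section also derives a PK reference standard. There, "The Decay corrected post-injection Reference Standard of syringe after injection into flask" is the amount left in the syringe multiplied by its factor.

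Protocol 9.5 tells sites to measure the syringe before and after administration and adds: "Apply decay correction if necessary and calculate the administered dose accordingly".

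SAP 8.2 summarizes "the decay corrected dose in mCi and MBq at time of administration" for the safety set, and SAP 12.1 plans a listing of it (16.2.5-6). SAP 9.1 computes percent dose excreted as "Sum of Radioactivity exerted per collection interval" over the administered dose.

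**The concern.** With a signed time difference in the exponent, the factor is below 1 for a reading taken before injection and above 1 for one taken after. Multiplying brings either reading to injection time. Dividing the residual moves it the wrong way, so too little is subtracted. The error has the same sign in every subject whose residual was not corrected, so it does not average out.

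The second branch is chosen only by the status of the residual. The factor-of-1 rule already handles corrected readings, so the branch adds nothing when both were corrected. When only the residual was corrected, it leaves the larger pre-injection reading undecayed.

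At stake are the exposure table and the dose listing. In the 10 PK subjects (Protocol 10.6), percent dose excreted and cumulative urinary recovery are also at stake if the administered dose in SAP 9.1 is this derived value. CL and Vss would be affected only if the external analyst uses it. SAP 7.7.4 says "These PK parameters will be derived by an external analyst then summarized for the PK blood set" but does not say which dose is supplied. Cmax, AUC, half-lives, MRT and all diagnostic-performance endpoints are untouched.

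**Working it through.** The section gives no numerical result to reproduce, so the formula was tested against known values.

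**Inputs from the documents:** half-life 110 min and both branches (SAP 5.5.10); planned activity 9 ± 1 mCi (Protocol 9.6). **Assumed, because the documents give none:** the syringe residual and the reading times.

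**Factor.** CF(t) = exp(ln 2 × t / 110), where t is reading time minus injection time in minutes. In the text, the 110 min appears outside the exponent. Taken literally, that gives 2^10/110 = 9.3 ten minutes after injection, which is not a usable decay factor, so it is treated as a typesetting matter and not counted as an error.

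**Which operation is right.** The factor exceeds 1 after injection, so the residual must be multiplied. The SAP's other uses agree: the post-flask residual is multiplied in 5.5.10, and 9.1 multiplies the blood, plasma and urine counts, which are measured after injection. The dose residual is the only term that is divided.

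**First branch, residual uncorrected.** Error = post × CF − post / CF subtracted too little, that is post × (CF − 1/CF). With 0.3 mCi as read:

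| Reading after injection | CF | CF − 1/CF | Overstatement | Share of 9 mCi |
|---|---|---|---|---|
| 5 min | 1.032 | 0.063 | 0.019 mCi | 0.2% |
| 10 min | 1.065 | 0.126 | 0.038 mCi | 0.4% |
| 20 min | 1.134 | 0.253 | 0.076 mCi | 0.8% |

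If the 0.3 mCi is instead the residual at injection time, the 10-minute error is 0.036 mCi.

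- To reach 1% of 9 mCi (0.09 mCi), the residual must be 0.09/0.126 = 0.71 mCi at 10 min, or 0.09/0.253 = 0.36 mCi at 20 min.
- An assumed extreme of 1 mCi read at 30 min gives 1 × 0.380 = 0.38 mCi, or 4.2%.
- With no correction at all, the 10-minute error would be 0.3 × 0.065 = 0.020 mCi. Dividing is therefore about twice as wrong as doing nothing.

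**Second branch, only the residual corrected.** Take a true dose of 9.0 mCi and a corrected residual of 0.3 mCi. The uncorrected pre-injection reading is 9.3/CF_pre, and the branch reports that minus 0.3.

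| Reading before injection | CF_pre | Pre reading | Reported dose | Dose error | Relative error in % excreted (9.0/reported − 1) |
|---|---|---|---|---|---|
| 10 min | 0.939 | 9.905 | 9.605 mCi | +6.7% | −6.3% |
| 20 min | 0.882 | 10.549 | 10.249 mCi | +13.9% | −12.2% |
| 30 min | 0.828 | 11.235 | 10.935 mCi | +21.5% | −17.7% |

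The reported value passes 10 mCi, the top of the stated range, at ln(10.3/9.3)/(ln 2/110) = 16.2 min. If both readings were corrected, the error is zero.

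**Check of the remedy.** Using pre × CF_pre − post × CF_post returned 9.000 mCi in every first-branch scenario run (pre reading 5, 10 or 30 min before; post reading 2, 5, 10 or 30 min after; residual 0.1 to 1.0 mCi at injection). In the mixed case, pre × CF_pre − post gives 9.3 − 0.3 = 9.0 mCi.

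**The case against.** The division cannot be defended on the text, but its size and reach can be disputed. For a modest residual the certain error is under 1%, against a window of 9 ± 1 mCi, and it falls on descriptive exposure summaries. That is correct, and it limits how much weight the point carries.

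The larger figures need a subject whose residual was corrected while the pre-injection reading was not. Protocol 9.6 refers measurement details to the Imaging Manual, which is not available here and may rule that out. The factor-of-1 sentence can also be read as one status for the pair, in which case plain subtraction is right for fully corrected pairs. Both observations stand. The second branch is therefore a gap whose frequency is unknown, not a demonstrated error in the data. Neither reading makes the branch correct if a mixed record does occur.

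The denominator in SAP 9.1 is called the administered dose, a term Protocol 9.5 uses for the site's own calculation. The link to urinary recovery is the natural reading but is not stated.

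Finally, a single formula needs the correction status of each reading, and it assumes that corrected readings were brought to injection time. The SAP's factor-of-1 rule and branches already rely on correction status and on that reference time, so the remedy adds no material new requirement.

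**Conclusion.** The concern holds. As written, SAP 5.5.10 overstates administered activity for every subject with a non-zero residual that was read after injection and not corrected, and it conflicts with its own treatment of the post-flask syringe. The effect is about 0.2% to 0.8% of 9 mCi for a 0.3 mCi residual read at 5 to 20 minutes, and reaches a few percent only with a large residual read late. The second branch is wrong only in the mixed case, where the overstatement would be 6.7% to 21.5% for pre-injection readings 10 to 30 minutes early. A dose within the stated range could then appear to lie above it. All residuals and times are assumptions, and the frequency of the mixed case is unknown. The conclusion about the primary and other diagnostic endpoints does not change. The formula should still be corrected, because it is applied to every dosed subject and the error is demonstrable from the text.

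**What to change.** Replace both branches with one formula: dose = pre × CF_pre − post × CF_post, with CF = exp(ln 2 × (reading time − injection time)/110 min) and the 110 min written inside the exponent. Set each CF to 1 only if that particular reading was already corrected to injection time. Add a sentence saying that the administered dose in SAP 9.1, and the dose given to the external PK analyst, is this derived value.

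The cost is one corrected formula and one clarifying sentence in the SAP, with the matching program change. No new data should be needed, since the current branches already depend on knowing which readings were corrected.

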#### 5.5.11. Lesion location defined from SUV values

There are three SUV values collected:  $SUV_{max}$ ,  $SUV_{peak}$  and  $SUV_{mean}$ . There are four locations that each of these SUV values could be present in: Bone, Soft tissue, prostate, and lymph nodes ('prostate gland right' and 'prostate gland left' were defined as a separate location from soft

tissue) as defined in Section 5.5.8. There are three reference values per subject at the following locations: Aorta, Liver and Muscle. For each tumor location that is not a reference location,  $SUV_R$  will be calculated against each reference as follows:

$$SUV_R = \frac{SUV_{MAX\_Tumor}}{SUV_{MEAN\_Re\ ference}}$$

Some subjects may have multiple SUV values within each location. These results will be averaged to derive one result per location and since there results should be similar per reviewer, only results for reviewer 1 will be used in any analyses. Subjects in Cohort B may have both a biopsied lesion and a tissue lesion within the same location. These SUV values should be summarized separately.

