### 5.5.7.1. Primary Endpoints and Pelvic Lymph Nodes

The primary endpoints of sensitivity and specificity are defined from lymph node imaging results and corresponding pelvic lymph node histology. For an imaging result to be deemed positive for this endpoint, the tissue must have first been removed from that corresponding area. This ensures that an imaging result has the ability to align with the results achieved from pathology. This will be applied to Cohort A subjects only.

PPV and NPV will also be calculated as secondary endpoints from the pelvic lymph nodes. The same definitions used below will apply.

Criteria for Positive PyL Imaging Result	Criteria for Lymph Node Dissection and Positive Histology
If Right or Left Pelvic Lymph Nodes Minimum Template = Positive and  • Tissue was removed from left template and total left nodes removed ≥1 and Template Left Pelvic LN Lesion Count	≥1 positive lymph node on right template if Template Right Pelvic LN Lesion Count from imaging is ≥0 or ≥1 positive lymph nodes on left template if Template Left Pelvic LN Lesion Count from
≥1 or  • Tissue was removed from right template and total right nodes removed ≥1 and Template Right Pelvic LN Lesion Count ≥1  or  Tissue was removed from Pre-sacral nodes and total pre-sacral nodes removed ≥1 and Pre-Sacral Pelvic LN Lesion Count ≥ 1	imaging is ≥0 or ≥1 positive lymph nodes on pre-sacral nodes if Pre-Sacral Pelvic LN Lesion Count from imaging is ≥0 or ≥1positive lymph nodes on other pelvic lymph nodes if Other Pelvic Lymph Node Count from imaging is ≥0
or Tissue was removed from Other lymph nodes and Total nodes removed >=1 and Other Pelvic LN Lesion Count ≥ 1 or	

If tissue was removed from right template and total right nodes removed ≥1 and resection included tissue along the external iliac artery and Right pelvic lymph node external iliac artery= positive or

If tissue was removed from left template and total left nodes removed ≥1 and resection included tissue along the external iliac artery and left pelvic lymph node external iliac artery= positive or

If tissue was removed from right template and total right nodes removed ≥1 and resection included tissue along the common iliac vein and Right pelvic lymph node common iliac vein= positive or

If tissue was removed from left template and total left nodes removed ≥1 and resection included tissue along the common iliac vein and left pelvic lymph node common iliac vein=positive or

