#### 5.5.8. Lesions Per Subject

The number of lesions detected on imaging categorized as bone, lymph nodes, soft tissue, and the prostate gland will be determined by each of the central imaging core lab independent readers. The sum of lesions per subject per tissue type and overall will be computed for each subject based on each reader's lesion count. This will be calculated from the F-DCFPyL PET/CT scan results as well as the conventional imaging results.

Bone	Soft Tissue	Lymph nodes	Prostate Gland
BN Skull	ST Brain	LN Cervical	ST Prostate Gland Left
BN Thorax	ST Neck	LN Supraclavicular	ST Prostate Gland Right
BN Spine	ST Lungs	LN Axillary	
BN Pelvis	ST Esophageal	LN Mediastinal	
BN Extremities	ST Liver	LN Hilar	
	ST Gall Bladder	LN Mesenteric	
	ST Spleen	LN Elbow	
	ST Pancreas	LN Popliteal	
	ST Adrenal	LN Peri-aortic/para-aortic	
	ST Kidney	LN Other, Non-Pelvic	
	ST Bladder	PLN Template Right	
	ST Prostate Bed	PLN Template Left	
	ST Seminal Vesicle	PLN Pre-Sacral	
	ST Skin	PLN Other, Pelvic	
	ST Muscle		
	ST Other		

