#### 7.8. Analysis of Exploratory Endpoints

Sensitivity and specificity of the prostate gland as well as  $SUV_{max}$ ,  $SUV_{peak}$  and  $SUV_r$  will all be analyzed on the evaluable set. Change in Management defined from the questionnaire will be summarized on the safety set. The PPV endpoint will be analyzed on the Change in Planned Protocol Procedure Set.

- SUVmax, SUVpeak, SUVmean, and volume will be summarized for each tissue location (bone, lymph nodes, soft tissue, and prostate gland) and each of the 3 central imaging core lab independent readers using the evaluable set from both cohorts. SUVr will be summarized in the same manner including a reference lesion also. A 95% confidence interval for the mean or distribution will be presented for each reader based on the assumption on normality defined in Section 7.2.
- Differences in the average across all 3 reviewers for SUVmax, SUVpeak, SUVr, SUVmean, and volume will be compared between histology outcomes using a t-test that assumes unequal variances. If the assumptions for the t-test are not met then a Wilcoxon rank sum test will be performed with corresponding exact 95% confidence intervals defined in section 7.2.
- The average SUVmax, SUVpeak, SUVr, SUVmean, and volume values across all reviewers will be compared between Gleason Score groups at time of radical prostatectomy, Baseline PSA groups and testosterone groups split at the median value. The comparisons of means between groups will be performed using a generalized linear model. If normality cannot be assumed then a Kruskal-Wallis test will be performed instead. Within each group a 95% confidence interval will be presented.
- Point estimates and two-sided 95% CIs for Specificity and Sensitivity will be computed from the prostate gland for Cohort A in the Evaluable Set. The normal approximation to the binomial distribution is planned assuming a null hypothesis of 0.5. If the assumptions are not met then confidence intervals derived from an Agresti-Coull exact test will be used (See Section 7.2). Results will be computed for each of the 3 central imaging core lab independent readers.

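### The SUV-by-histology comparison does not limit Cohort A values to sampled tissue, so uptake in unresected nodes can be labelled by pelvic-node pathology

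*SAP*

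**What the plan says.** SAP 5.5.11 recognises four SUV locations, "Bone, Soft tissue, prostate, and lymph nodes", and takes their content from the tissue table ("as defined in Section 5.5.8"). In that table the lymph-node column holds fourteen regions. Ten are non-pelvic, running from cervical nodes through "LN Supraclavicular" to para-aortic nodes and "LN Other, Non-Pelvic". Four are pelvic: right template, left template, pre-sacral and other pelvic.

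Where a subject has several values in a location, SAP 5.5.11 directs: "These results will be averaged to derive one result per location". No condition on resection is attached.

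Under SAP 7.8 the SUV measures "will all be analyzed on the evaluable set", and SUVmax, SUVpeak, SUVr, SUVmean and volume "will be compared between histology outcomes using a t-test that assumes unequal variances", with a Wilcoxon rank sum test as fallback. SAP 3.2.3 lists this as an exploratory endpoint covering both cohorts.

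The plan handles unsampled tissue differently elsewhere. For a positive PET call on the primary endpoint, SAP 5.5.7.1 requires that "the tissue must have first been removed from that corresponding area". Protocol 12.3.1 leaves PET-positive nodes in unresected areas out of the diagnostic classification because they have no pathology. In Cohort B, SAP 5.5.11 keeps the biopsied lesion apart from other lesions in the same location.

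**The concern.** The exploratory endpoint asks whether tracer uptake differs between positive and negative histology. That question can be answered only if each SUV comes from the tissue the pathologist examined. In Cohort A the planned pathology covers the prostate gland and the removed pelvic nodes, whereas the PET field runs from mid-thigh to the top of the skull (Protocol 10.1.1). Nodes that nobody samples are therefore imaged and, under the averaging rule, enter the nodal SUV.

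A man with negative pelvic nodes and an avid para-aortic node would then contribute that node's uptake to the histology-negative group. A man with a positive pelvic node and an avid para-aortic node would contribute a blend of the two to the positive group. In neither case does the SUV describe the tissue that determined the label. The result would be hard to interpret, and a programmer would have to invent the pairing.

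**Working it through.** The documents state no figure for this comparison, so there is nothing to reproduce. The check traces the definitions and then illustrates the arithmetic.

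**Tracing the definitions**

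1. Nodal location (SAP 5.5.8): 14 regions, less 4 pelvic groups, leaves 10 non-pelvic regions.
2. Aggregation (SAP 5.5.11): the mean of all values in the location, with no restriction.
3. Comparison (SAP 7.8): between histology outcomes, again with no restriction. The text does not say whether node, gland or biopsy pathology is meant for a given location.
4. Available pathology in Cohort A (Protocol 10.5): prostate gland and pelvic nodes. Bone, other soft tissue and non-pelvic nodes have no planned pathology.
5. Safeguards elsewhere: a tissue-removed rule for the primary endpoint and lesion separation in Cohort B. Neither is carried to the Cohort A SUV comparison.

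**One subject (assumed SUVs)**

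A resected pelvic node at 5 and an unresected para-aortic node at 20 give (5 + 20)/2 = 12.5, labelled by the pelvic result. With no pelvic uptake, negative pelvic pathology and the same para-aortic node, the man contributes 20 to the negative group.

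**Group level (assumed SUVs)**

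Let m be the pelvic SUV in a group and n the number of pelvic nodes averaged. Let q be the share of the group with one unresected node, and x that node's SUV. The group mean becomes m + q(x − m)/(n + 1). Assume m = 10 in the positive group, m = 4 in the negative group and x = 15. The difference without contamination is 6.0.

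With the same q in both groups, the difference is 6 × [1 − q/(n + 1)]:

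| q | n = 1 | n = 2 |
|---|---|---|
| 5% | 5.85 | 5.90 |
| 10% | 5.70 | 5.80 |
| 20% | 5.40 | 5.60 |
| 30% | 5.10 | 5.40 |

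With different shares and n = 1, the positive mean is 10 + 2.5q₊ and the negative mean is 4 + 5.5q₋, so the difference is 6 + 2.5q₊ − 5.5q₋.

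- q₊ = 20%, q₋ = 0: 6 + 0.5 = 6.5, an inflated contrast.
- q₊ = 0, q₋ = 20%: 6 − 1.1 = 4.9, a diluted contrast.

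The direction therefore depends on how extra-pelvic uptake is distributed between the groups. The documents give neither q nor any SUV.

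**The case against.** Several points on the other side carry weight.

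- **The text is partly silent.** The SAP never says in words that unresected nodes are included, and it does not name the paired histology result. Protocol 12.5.2.3 goes on from histopathology to the Gleason score of the dominant prostate nodule, so gland pathology might be the intended anchor. The Imaging Manual or Review Charter, not available here, might limit which lesions receive an SUV. This stands as a limit on certainty. However, SAP 5.5.11 and 7.8 cite no such limit, and pairing nodal uptake with gland pathology would be no better matched.
- **Some affected men drop out of the analysis.** Under SAP 4.1, 4.2, 5.4.3 and 5.4.4 the physician may change the planned procedure after PET, and Cohort A men who then have no surgery are not evaluable. A man with distant uptake is an obvious candidate. This lowers the number affected, but the change is optional, so it does not remove the problem.
- **The rank-test fallback.** A Wilcoxon test is less sensitive to a few extreme SUVs. It does not correct a wrong label.
- **The analysis is exploratory.** It carries no success rule, and the tissue-removed rule protects primary sensitivity and specificity. This stands in full.

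A reader might go further and infer that the contrast is biased toward no difference, that the negative-group mean is inflated by a known amount, or that an SUV cut-off taken from the analysis would be wrong. The documents support none of these. Positive men's values are averaged over the same regions, the frequencies and SUVs are not given, and no SUV cut-off is planned. Nor should the pooling be read as covering every node in the body: popliteal nodes lie outside the scan field and elbow nodes may.

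**Conclusion.** The point holds as a mismatch of definitions in an exploratory analysis. Following the averaging rule as written allows unsampled nodal uptake in Cohort A to be labelled by pathology from other tissue, and it leaves Cohort A bone and other soft-tissue SUVs with no planned histology to pair with. That conclusion needs no numerical assumption. It does assume that no document outside the protocol and SAP restricts which lesions receive an SUV.

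The size and direction of the bias cannot be determined. The illustrative differences, 5.10 to 5.90 against 6.0 under equal contamination and 4.9 or 6.5 under one-sided contamination, rest wholly on assumed SUVs and shares. They show only that the effect can be modest and can go either way. The primary endpoints are unaffected. The correction is worth making because it is cheap and the plan already applies the same principle elsewhere.

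**What to change.** Amend SAP 5.5.11 and 7.8 so that, for the histology comparison only, one value per subject per tissue is used and its histology result is named:

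- **Cohort A nodes:** the average over the pelvic regions (right template, left template, pre-sacral, other pelvic) from which tissue was removed, paired with the subject-level pelvic-node histology of SAP 5.5.7.1.
- **Cohort A gland:** the gland SUV, paired with the subject-level gland histology of SAP 5.5.7.3.
- **Cohort B:** the biopsied lesion, paired with its biopsy result.

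Exclude Cohort A bone, other soft-tissue and non-pelvic nodal SUVs from this comparison. Keep the all-lesion average for the descriptive uptake-by-location tables.

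If region-level or side-level pairs are preferred, each man contributes several correlated values and the independent-samples tests in SAP 7.8 no longer fit. The analysis would then have to account for clustering within subject.

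The cost is SAP wording and a filter on the region and resection data already used in SAP 5.5.7.1. No new data are needed. The downside is that fewer SUV values enter the comparison.
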